7.1.2.2 STUDY PRODUCT ADMINISTRATION

Detailed instructions for thawing the cells and preparing for administration are written in the manual titled "Descartes-30 Product Preparation, Storage and Administration Manual".

Pre-medication for the cell infusion is recommended and should be given approximately 30 minutes prior to infusion. The recommended pre-medications are acetaminophen 500-1000 mg orally and diphenhydramine 25-50 mg orally or intravenous. Following parameters should be recorded within 10 min before infusion to be used as baseline for determining infusion reaction as defined in Section 8.1.2: FiO₂, positive end-expiratory pressure (PEEP)], types and doses of vasoactive drugs, and vital signs [include core temperature, mean arterial pressure (mmHg), pulse (beats/min), respiratory rate (breaths/min)].

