SEM	Standard Error of the Mean
SM	Starting Materials
SOFA	Sequential Organ Failure Assessment
SUSAR	Serious Unexpected Adverse Reaction
TK	Toxicokinetic(s)
WHO	World Health Organization

PROTOCOL SYNOPSIS

Title: Phase I/IIa Study of Descartes-30 in Acute Respiratory Distress Syndrome.
Study Description: This is a Phase I/IIa, open-label, emergency study to test the safety of Descartes-30 cells in patients with acute respiratory distress syndrome (ARDS) and severe pneumonia (PNA). The cell product consists of Mesenchymal Stem Cells (MSCs) engineered to express DNase1 and DNase1L3 to degrade Neutrophil Extracellular Traps (NETs), which are a cardinal and causative feature of ARDS. In the dose escalation arm (Arm 1), the study will enroll three patients with ARDS into each of four successive dose levels to test escalating doses of Descartes-30. An additional 12 patients with ARDS (ARDS Cohort) and 12 patients with severe pneumonia (PNA Cohort) will be enrolled into a dose expansion arm (Arm 2).
Objectives: **The primary objective** is to assess the safety of Descartes-30 in patients with moderate-to-severe ARDS. Safety will be determined principally by assessment of adverse events (AEs) and serious adverse events (SAEs).
[REDACTED]

The exploratory objectives are:
[REDACTED]

Endpoints: The primary endpoint is the Maximum Tolerated Dose (MTD) defined as the highest Dose Level at which no more than one patient has shown Dose-Limiting Toxicity (DLT).
[REDACTED]

Study Population:

The study will enroll about 36 patients: about 12 patients in a dose escalation arm and about 24 patients in an expansion arm. The major eligibility criteria are as follows: (1) 18 years or older; (2) respiratory failure; (3) ARDS diagnosis per Berlin criteria within 14 days of first cell infusion OR severe PNA per ATS/IATS criteria within 7 days of first cell infusion; (4) maximal medical therapy already in place, in the opinion of the treating physician; (5) informed consent from participant or health care proxy. Patients will be excluded if they (1) are moribund with expected survival <24 hours, (2) are pregnant (3) have severe baseline morbidity prior to diagnosis of ARDS or PNA, (4) have used Pulmozyme® (dornase alfa) after diagnosis of ARDS or PNA. For complete list of inclusion and exclusion criteria, see Full Protocol.

Phase:

I/IIa

Study Site:

Multi-center

Study Design:

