4.5 DOSE ESCALATION STOPPING RULES

The Medical Monitor will apply the following rules to determine if it is safe to proceed to the next Dose Level, or if dose escalation should stop. Pre-specified rules for pausing or stopping the whole study are described in Section 8.5 and rules for individual patient withdrawal are described in Section 8.4.

Should one of three patients in a Dose Level experience dose-limiting toxicity (DLT, see Section 8.1.2 for definition) within 7 days after receiving the first dose of the cells that is considered probably or definitely related to Descartes-30, 3 more patients will be enrolled and treated at that Dose Level. If only 1/6 of patients at that Dose Level has a DLT, and if the medical monitor agrees, treatment will proceed to the next higher Dose Level. If 2 or more out of 3 to 6 patients develop a DLT, no further patients will be dosed at that dose level. The MTD will be defined as the highest dose at which a maximum of 1 of 6 patients has a DLT. In Arm 2, up to 12 more patients who meet the eligibility criteria may be treated in each cohort (ARDS and PNA) at a dose up to MTD, provided that the medical monitor approves the enrollment of each such patient based on ongoing review of the cumulative safety data.

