7.1.2.3 POST-INFUSION OBSERVATION

There is a theoretical risk that MSCs can aggregate in pulmonary vasculature resulting in respiratory and hemodynamic instability. Thus, during and up to 4 hours (Arm 1) or 1 hour (Arm 2) following completion of infusion, the patient should be observed by a qualified study team staff to assess any dose-limiting infusion-related reactions, which are defined in Section 8.1.2. Patient's vital signs (i.e., core temperature, mean arterial pressure (mmHg), pulse (beats/min), respiratory rate (breaths/min), and transcutaneous oxygen saturation) should be monitored at least hourly (± 15 minutes or more frequently if clinically indicated). If applicable, changes in ventilation variables (i.e., type of ventilation (CPAP, BiPAP, or intubation), ventilation rate, pulse, tidal volume, positive end-expiratory pressure (PEEP)), vasoactive drugs and renal support will be recorded. These findings will be documented in the e-CRF.

Following the mandatory observation, the Investigator will decide if continuous monitoring can be discontinued. If the vital signs are not satisfactory and not stable for 4 hours (Arm 1) or 1 hour (Arm 2) post-infusion, vital signs will continue to be monitored at a minimum of every hour (± 15 minutes) or as clinically indicated until stable. If a reaction is suspected, the sequence of clinical events should be documented in detail into the e-CRF.

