8.1.2 DOSE LIMITING TOXICITY (DLT)

Following reactions within 4 hours of Descartes-30 infusion will be considered as DLT:

1. Addition of a third vasopressor
2. Increase in vasopressor dose over baseline greater than or equal to the following:
 - a. Norepinephrine: 1.5 μ g/kg per min
 - b. Phenylephrine: 100 μ g/kg per min
 - c. Dopamine: 10 μ g/kg per min
 - d. Epinephrine: 1 μ g/kg per min
 - e. Vasopressin: 0.04 IU/min
3. Hypoxemia requiring an increase over baseline in FiO_2 of ≥ 0.2 and/or increase in positive end-expiratory airway pressure level of 5 cm H₂O or more to maintain transcutaneous oxygen saturations in an acceptable range based on PI's discretion
4. New cardiac arrhythmia requiring cardioversion (chemical or electrical)
5. New ventricular tachycardia, ventricular fibrillation, or asystole
6. Death

Also, any Grade 3-5 toxicity probably or definitely attributed to Descartes-30 will be a DLT.

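### DLT item 3 cannot be met on FiO2 when the pre-infusion FiO2 is above 0.80, leaves high-flow patients above 0.80 without a clearly defined limb, and relies on a post-infusion FiO2 that section 7.1.2.3 does not list

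*Combined protocol and SAP*

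**What the plan says.** **The DLT list.** Section 8.1.2 names six reactions that are DLTs if they occur within 4 hours of infusion, with no attribution condition. Item 3 begins "Hypoxemia requiring an increase over baseline in" FiO2. Its thresholds are a rise of at least 0.2 in FiO2 and/or of 5 cm H2O or more in PEEP, needed to keep saturation in a range the PI accepts. Apart from death, it is the only respiratory item. A separate sentence adds that "any Grade 3-5 toxicity probably or definitely attributed to Descartes-30 will be a DLT".

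**The baseline.** Under 7.1.2.2, FiO2, PEEP, vasoactive drugs and vital signs "should be recorded within 10 min before infusion to be used as baseline for determining infusion reaction".

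**After infusion.** Section 7.1.2.3 gives the reason for observation: "There is a theoretical risk that MSCs can aggregate in pulmonary vasculature resulting in respiratory and hemodynamic instability". Vital signs, including saturation, are monitored at least hourly for 4 hours in Arm 1 and 1 hour in Arm 2. The respiratory variables to be recorded, where applicable, are "changes in ventilation variables (i.e., type of ventilation (CPAP, BiPAP, or intubation), ventilation rate, pulse, tidal volume, positive end-expiratory pressure (PEEP"). Detailed documentation is required once a reaction is suspected.

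**Who is eligible.** Section 4.2 admits ARDS of any Berlin severity. Section 5.1 lets high flow at 30 L/min or more satisfy the PEEP requirement. Nothing in 5.1, 5.2 or the stability check in 7.1.2.1 caps FiO2.

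**How DLTs are used.** In 4.5, one DLT in three patients leads to three more patients if it is judged probably or definitely related. The section then says "If 2 or more out of 3 to 6 patients develop a DLT, no further patients will be dosed at that dose level" and "The MTD will be defined as the highest dose at which a maximum of 1 of 6 patients has a DLT". The synopsis defines the MTD, the primary endpoint, as the "highest Dose Level at which no more than one patient has shown Dose-Limiting Toxicity". Under 8.1.3, an infusion reaction as defined in 8.1.2 is an SAE. Section 8.3 requires SAEs to be reported within 24 hours whatever the suspected cause.

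**The concern.** Item 3 is the criterion aimed at the product risk that 7.1.2.3 names. It is measured as a change from baseline on a scale with a ceiling, so it is least able to register an event in the patients with the least respiratory reserve. A high-flow patient above 0.80 who desaturates despite FiO2 1.0 has deteriorated, yet meets neither limb as written.

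There is also a data problem. The baseline FiO2 is recorded expressly for this comparison, but the second reading is not on the post-infusion list.

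The 4-hour list is the part of the DLT definition that does not ask whether the product caused the event. In severe ARDS attribution is hard to judge, so losing that route puts more weight on individual judgement, both for DLTs and for SAE status.

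**Working it through.** The plan gives no figure to reproduce here; 9.1 says no formal sample size calculation was done. The check uses the thresholds in 8.1.2, the baseline in 7.1.2.2 and the recording lists in 6.2 and 7.1.2.3.

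**1. Ceiling.** Room to rise = 1.00 - baseline FiO2, to be compared with 0.20.

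| Baseline FiO2 | Room to rise | FiO2 limb reachable |
|---|---|---|
| 0.60 | 0.40 | yes |
| 0.80 | 0.20 | yes, just |
| 0.81 | 0.19 | no |
| 0.90 | 0.10 | no |
| 1.00 | 0.00 | no |

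**2. Limbs that are clearly defined.**

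| Support before infusion | FiO2 0.80 or below | FiO2 above 0.80 |
|---|---|---|
| Set PEEP | both | PEEP only |
| High flow | FiO2 only | none |

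For high flow the PEEP limb is undefined rather than closed. A move to CPAP, BiPAP or intubation could be read as a PEEP increase, but the text gives no baseline from which to measure it. Two sites could score the same escalation differently.

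**3. Which patients.** If PaO2 is 60 to 80 mmHg (an assumption), then at FiO2 0.80 the ratio is 60/0.80 = 75 to 80/0.80 = 100. Above 0.80 it is lower still. This lies in the Severe class of Appendix C (100 or below). The documents do not say how many such patients will be enrolled, or how many will be on high flow.

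**4. Recording.** Before infusion, FiO2 and PEEP are both listed (7.1.2.2). After infusion, PEEP and type of ventilation are listed; FiO2 and high flow are not (7.1.2.3). The PaO2/FiO2 assessment on infusion days is done before the product is given (6.2). This gap touches every patient scored on the FiO2 limb, not only those above 0.80.

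**5. Effect on the dose-level count.** Take a cohort of three with two 4-hour respiratory events, neither judged probably or definitely related. One is in a high-flow patient above 0.80 who desaturates despite FiO2 1.0.

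| Reading of 4.5 | Both events scored | Item 3 as written |
|---|---|---|
| Relatedness qualifier applies only to the expansion step | 2/3: level stops | 1/3: no stop, and no expansion because the event is not attributed |
| Qualifier applies throughout | 0/3 | 0/3 |

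The count changes only under the first reading.

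**6. Illustration under the first reading.** Let each patient have probability p of an unattributed 4-hour respiratory event, and let a share s of patients be impossible to score. The scored count X is Binomial(3, q) with q = p(1 - s), and P(X ≥ 2) = 3q²(1 - q) + q³.

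| p | s = 0 | s = 1/6 | s = 1/3 |
|---|---|---|---|
| 0.2 | 0.104 | 0.074 | 0.049 |
| 0.4 | 0.352 | 0.259 | 0.175 |

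Both p and s are assumed; the documents give neither. The model also treats every event in the share s as lost, although some would involve an escalation of support that a site might score. The table shows direction only.

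**The case against.** The strongest reply is that little escapes. Four parts of it stand.

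- Grade 3-5 events judged probably or definitely related are DLTs whatever the baseline FiO2, and the expansion step in 4.5 already requires that attribution. Only unattributed events are at issue.
- The sentences in 4.5 that follow the expansion step can fairly be read as continuing the same algorithm, with the relatedness qualifier carried through. On that reading the ceiling has little effect on the count. The text does not settle which reading is meant.
- Section 4.4 requires the PI and Medical Monitor to review each Arm 1 patient before the next is infused, with first infusions at least 7 days apart. The monitor must also document a cumulative review before the next dose level. A severe desaturation would come before both reviews whether or not item 3 is ticked.
- The patient is protected in other ways: the stability check and delay rule (7.1.2.1), hourly saturation (7.1.2.3) and the off-treatment criteria (7.1.2.5).

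A reader might therefore be tempted to infer that respiratory toxicity in these patients goes unseen, or that the MTD will be set too high. The documents support neither inference, given these routes and the unknown share of patients affected.

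It can also be said that staff are told to look for the reactions defined in 8.1.2, and that site charts may hold FiO2. That softens the recording gap but does not close it. Detailed documentation begins only once a reaction is suspected, so it cannot serve as routine detection.

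**Conclusion.** The point holds in limited form. Above a pre-infusion FiO2 of 0.80 the FiO2 limb cannot be met. Ventilated patients keep the PEEP limb, and high-flow patients have no clearly defined limb. Separately, the post-infusion FiO2 that item 3 needs is not on the list in 7.1.2.3.

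What these patients lose is DLT scoring that does not depend on attribution, together with automatic SAE classification. New intubation or ECMO can still be reported under the other criteria in 8.1.3, but by judgement. An effect on the stopping count or the MTD requires unattributed events and the reading of 4.5 in which the qualifier does not carry through.

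The ceiling and the recording gap follow from the text alone. The size of the effect cannot be established from the documents, so the point is minor to moderate. The synopsis describes Arm 1 monitoring in the past tense. If Arm 1 is complete, the change still bears on SAE classification in Arm 2 and on the cumulative safety data that the medical monitor uses to approve each Arm 2 patient (4.5).

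**What to change.** Keep the baseline, the 4-hour window and both thresholds.

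1. In 7.1.2.3, add FiO2 and oxygen device (including high flow) to what is recorded with the hourly saturation.
2. In 8.1.2, add to item 3:

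> If pre-infusion FiO2 is above 0.80, the item is also met within 4 hours by saturation below the PI's acceptable range despite FiO2 1.0, or by hypoxemia requiring escalation from high flow to CPAP, BiPAP or intubation, or new intubation or ECMO.

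Leave item 3 unchanged at FiO2 0.80 or below, where the FiO2 limb works. Do not score baseline PEEP as 0 for every patient without a set PEEP. That sits badly with 5.1, which accepts high flow as meeting the PEEP requirement, and it would make a move from high flow at FiO2 0.40 to CPAP 5 for hypoxemia an automatic DLT and SAE.

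**Cost.** One sentence and two fields. At the hourly minimum with three infusions each, the readings number 4 x 3 x 12 = 144 in Arm 1 and 1 x 3 x 24 = 72 in Arm 2, or 216 in all. In Arm 2 the required observation is 1 hour, so a single reading does not cover the 4-hour window; later events there would still depend on a reaction being suspected.

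**Downside.** There will be a few more DLT and SAE records in the most severe patients, some of them disease progression. If the qualifier in 4.5 does not carry through, these would count toward stopping a dose level.

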7.1.2.3 POST-INFUSION OBSERVATION

There is a theoretical risk that MSCs can aggregate in pulmonary vasculature resulting in respiratory and hemodynamic instability. Thus, during and up to 4 hours (Arm 1) or 1 hour (Arm 2) following completion of infusion, the patient should be observed by a qualified study team staff to assess any dose-limiting infusion-related reactions, which are defined in Section 8.1.2. Patient's vital signs (i.e., core temperature, mean arterial pressure (mmHg), pulse (beats/min), respiratory rate (breaths/min), and transcutaneous oxygen saturation) should be monitored at least hourly (± 15 minutes or more frequently if clinically indicated). If applicable, changes in ventilation variables (i.e., type of ventilation (CPAP, BiPAP, or intubation), ventilation rate, pulse, tidal volume, positive end-expiratory pressure (PEEP)), vasoactive drugs and renal support will be recorded. These findings will be documented in the e-CRF.

Following the mandatory observation, the Investigator will decide if continuous monitoring can be discontinued. If the vital signs are not satisfactory and not stable for 4 hours (Arm 1) or 1 hour (Arm 2) post-infusion, vital signs will continue to be monitored at a minimum of every hour (± 15 minutes) or as clinically indicated until stable. If a reaction is suspected, the sequence of clinical events should be documented in detail into the e-CRF.

7.1.2.4 GUIDANCE FOR DISCONTINUATION OF MECHANICAL VENTILATION

The following weaning trial guidelines should be followed for patients who require mechanical ventilation at baseline or during the trial:

Patients should be assessed for the following weaning readiness criteria:

- PaO₂/FiO₂ >300 after 1 hour with PEEP <10 and FiO₂ <0.5
- Values of both PEEP and FiO₂ values are lower from previous day
- The patient is not receiving neuromuscular blocking agents
- The patient is exhibiting inspiratory efforts
- Systolic arterial pressure ≥ 90 mmHg without vasopressor support or minimal vasopressor support (i.e., ≤ 5 μ g/kg/min dopamine or dobutamine)

If these criteria are met, a spontaneous breathing trial (SBT) procedure and assessment for unassisted breathing should be performed. The SBT will take place for up to 120 minutes of spontaneous breathing with $\text{FiO}_2 < 0.5$ using any of the following approaches:

- Pressure support (PS) $\leq 5 \text{ cmH}_2\text{O}$, PEEP $\leq 5 \text{ cmH}_2\text{O}$
- Continuous positive airway pressure (CPAP) $\leq 5 \text{ cmH}_2\text{O}$
- T-piece
- Tracheotomy mask

If all criteria below are met for the last 30 minutes of the trial, the SBT will be reported as “successful” and ventilation support will be removed:

- $\text{SpO}_2 \geq 90\%$ and/or $\text{PaO}_2 \geq 60 \text{ mmHg}$
- Respiratory rate $\leq 35/\text{min}$
- No respiratory distress (defined as ≥ 2 of the following):
 - Heart rate $\geq 120\%$ of the rate at 06:00 ($\leq 5 \text{ min}$ at $\geq 120\%$ may be tolerated)
 - Marked use of accessory muscles
 - Abdominal paradox
 - Diaphoresis
 - Marked subjective dyspnea

If above criteria are not met, the SBT will be reported as “unsuccessful” and previous ventilator settings will be initiated. The patient should be reassessed for weaning the following day.

Patients will be reported as “ventilator free” after two consecutive calendar days of “unassisted breathing”. “Unassisted breathing” will be defined as any of the following:

- Spontaneously breathing with face mask, nasal cannula or room air
- T-piece breathing
- Tracheostomy mask breathing
- CPAP ≤ 5 without Pressure Support or intermittent mandatory ventilation assistance
- Use of CPAP or bi-level positive airway pressure solely for sleep apnea management

Please discuss with Sponsor if institutional ventilator weaning policy conflicts significantly with the above criteria.

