7.1.3 RETURN OR DESTRUCTION OF STUDY PRODUCT

7.2 SAFETY MONITORING PERIOD

7.2.1 CONCOMITANT MEDICATIONS

Any medication the patient takes other than the study product between screening and Day 28 (or last day of stay in the administering unit, whichever comes earlier), including herbal and other non-traditional remedies, is considered to be a concomitant medication. All concomitant medications must be recorded in the e-CRF **except for**: nutritional and volume therapy, electrolyte support, vitamins, and supportive therapies such as artificial tears, ointments, etc.

The following information must be recorded in the e-CRF for each concomitant medication: generic name, route of administration, start date, stop date, dosage and indication. If a patient is discharged from the administering unit prior to Day 28 then the patient must be instructed that the Investigator may ask about additional medication up to Day 28.

The choice of concomitant medications or therapies will be left to the Investigator's discretion. The supportive care will be provided based on the local institute's ICU, IMC, and acute care floor standards. Any DNase containing therapy should be avoided unless it is absolutely medically necessary.

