9 STATISTICAL CONSIDERATIONS

9.1 SAMPLE SIZE

As this is an early-phase open-label study with a dose-escalation regimen, no formal sample size calculations have been performed. The sample size has been selected for practical considerations and is based upon experience from similar past clinical study designs. The selected number of subjects is considered sufficient to achieve the clinical study objectives, which are not of an inferential statistical nature.

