9.3 EFFICACY

Efficacy will be assessed by descriptive statistics of treatment response per clinical endpoints that are frequently used in ARDS outcome trials such as all-cause mortality at Day 28, change in SOFA score from baseline, change in WHO Ordinal Score, change in PaO₂ / FiO₂ ratio (arterial partial pressure of O₂ / fraction of inspired O₂) from 0 to 96 hours after first dose, to determine all-cause mortality at Day 28 for patients diagnosed with COVID-19, change in PaO₂ / FiO₂ ratio from 0 to 24, 48, and 96 hours after first dose, days free of renal support (for patients receiving renal support at baseline), days free of vasoactive support (for patients receiving at least one vasopressor at baseline), days free of mechanical ventilation, days with a fever (temperature $\geq 38^{\circ}\text{C}$) number of ICU-free days, and number of days in hospital.

Days free of mechanical ventilation is defined as the number of calendar days during which the patient is ventilator-free including two unassisted breathing (UAB) days to Day 28, assuming that a patient survives for at least two consecutive calendar days after initiating UAB.

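### The weaning-readiness rule requires PEEP and FiO₂ both to have fallen since the day before, so patients stable on low settings do not trigger a breathing trial

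*Combined protocol and SAP*

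**What the plan says.** Section 7.1.2.4 opens with "The following weaning trial guidelines should be followed for patients who require mechanical ventilation at baseline or during the trial". It then gives five readiness criteria:

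1. PaO₂/FiO₂ above 300 after one hour, with PEEP below 10 and FiO₂ below 0.5
2. "Values of both PEEP and FiO₂ values are lower from previous day"
3. No neuromuscular blockers
4. Inspiratory efforts present
5. Adequate systolic pressure on no or minimal vasopressor support

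The consequence follows: "If these criteria are met, a spontaneous breathing trial (SBT) procedure and assessment for unassisted breathing should be performed". Nothing says that any one criterion is enough. Item 2 has no allowance for equal values and no exemption for settings that are already low.

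The SBT itself may be run on pressure support with PEEP up to 5 cmH₂O, on CPAP up to 5, on a T-piece or on a tracheotomy mask. After an unsuccessful SBT, "previous ventilator settings will be initiated. The patient should be reassessed for weaning the following day". The section closes with "Please discuss with Sponsor if institutional ventilator weaning policy conflicts significantly with the above criteria". Separately, Section 7.2.1 states: "The supportive care will be provided based on the local institute's ICU, IMC, and acute care floor standards".

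The outcome that depends on the timing of weaning is in Section 9.3: "Days free of mechanical ventilation is defined as the number of calendar days during which the patient is ventilator-free", counted to Day 28 and including the two qualifying days of unassisted breathing.

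**The concern.** Item 2 tests for change since yesterday, whereas item 1 already tests whether the settings are low enough. A patient can satisfy item 1 and still fail item 2 because the settings have stopped moving. This catches patients with both settings unchanged at low values and patients with only one setting lowered. It also catches patients put back on their earlier settings after an unsuccessful SBT and left there, which is a special case of unchanged settings.

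At a site that follows the item literally, the result is a later SBT for someone who may be ready for one. That can mean more time on the ventilator and fewer ventilator-free days, caused by the protocol's wording and not by the patient's course.

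**Working it through.** The plan gives no figure to reproduce on this point, so the check is one of logic followed by simple arithmetic.

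**Which patients trigger an SBT**

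Inputs from Section 7.1.2.4:
- Item 1: PaO₂/FiO₂ > 300, PEEP < 10, FiO₂ < 0.5.
- Item 2 as written: PEEP today < PEEP yesterday and FiO₂ today < FiO₂ yesterday.
- Item 2 as proposed: replace each < with ≤.

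Assumptions: items 3 to 5 are met; FiO₂ today is 0.40; PaO₂ is 130 mmHg except in the last row. PaO₂/FiO₂ is then 130/0.40 = 325, or 100/0.40 = 250 in the last row. The patient is on pressure support or mandatory breaths, because CPAP at 5 or below without such assistance already counts as unassisted breathing.

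| PEEP / FiO₂ yesterday → today | Item 1 | SBT as written | SBT as proposed |
|---|---|---|---|
| 5 / 0.40 → 5 / 0.40 | met | no | yes |
| 8 / 0.40 → 8 / 0.40 | met | no | yes |
| 8 / 0.40 → 5 / 0.40 | met | no | yes |
| 5 / 0.45 → 5 / 0.40 | met | no | yes |
| 8 / 0.45 → 5 / 0.40 | met | yes | yes |
| 5 / 0.40 → 8 / 0.40 | met | no | no |
| 5 / 0.40 → 5 / 0.40, PaO₂ 100 | not met | no | no |

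The first four rows are the patients at issue. In the first, the patient is already at a PEEP the SBT allows. The sixth row shows that the proposed wording still stops a patient whose support was raised; the last shows that item 1 is not loosened.

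**Effect on one patient's ventilator-free days**

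If unassisted breathing starts on Day d and is sustained, with survival to Day 28, the count is 28 − d + 1:
- d = 8: 28 − 8 + 1 = 21
- d = 9: 28 − 9 + 1 = 20
- d = 10: 28 − 10 + 1 = 19

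Each day of delay costs one day, provided the delayed SBT would have succeeded.

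**Effect on a cohort mean**

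Each Arm 2 cohort has about 12 patients (Synopsis and Section 4.2). The fall in the mean is (patients delayed × days delayed)/12. The patient counts and delays below are assumptions, not figures from the documents.

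| Patients delayed | Days each | Fall in mean (days) |
|---|---|---|
| 1 | 1 | 1/12 = 0.08 |
| 3 | 1 | 3/12 = 0.25 |
| 3 | 2 | 6/12 = 0.50 |
| 6 | 2 | 12/12 = 1.00 |

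**The case against.** The strongest reply is that the plan already copes. The section is headed as guidance. It says when an SBT should be done and does not forbid one otherwise. Local standards govern supportive care, and a site with a conflicting policy is asked to raise it. All of this is true, and it confines the concern to sites that follow the item literally and raise no conflict. It does not supply a reading in which unchanged counts as lower. The opening line still asks for the guidelines to be followed, and the discussion route depends on a site noticing a significant conflict.

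A second reply is that clinicians set PEEP and FiO₂ and can often lower them the same day. At FiO₂ 0.40, item 1 implies PaO₂ above 0.40 × 300 = 120 mmHg, and at 0.30 above 90 mmHg, while the SBT can be passed at 60 mmHg. There is often room to reduce FiO₂. That shortens many delays, but item 2 needs both settings to fall, so a patient whose PEEP is already at its floor stays excluded.

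Third, next-day reassessment after a failed SBT is not contradicted, since it may properly find the patient not ready. That stands. Even so, if the earlier settings are resumed and left alone, item 2 cannot be met that day.

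Fourth, the authors may have meant to require improvement and not merely absence of worsening. The documents do not say. Relaxing the item is a clinical change, and the sponsor's clinicians should confirm it.

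Finally, the cohort figures are illustrative. The 1.00-day case needs half a cohort to be ventilated, held back by item 2 alone for two days, and then to pass. Entry allows noninvasive ventilation or high-flow oxygen (Section 5.1), and severe pneumonia can qualify on minor criteria (Appendix C), so many patients may never be on this pathway.

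**Conclusion.** The concern holds as a minor, optional improvement. The wording and its effect on the SBT trigger are clear. Whether any site would delay an SBT because of it is unknown.

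If it happens, the cost is one ventilator-free day per patient per day of delay, and 0.08 to 1.00 day in a 12-patient cohort mean over the assumed range. This rests on the delayed SBT being one that would have succeeded, on sustained unassisted breathing, and on survival to Day 28.

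The reach is limited. Ventilator-free days are summarised descriptively, and Section 9.1 describes the study objectives as ones "which are not of an inferential statistical nature". The MTD, the DLT rules and the primary safety objective do not depend on the item, and no patient breathing unassisted is misclassified.

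**What to change.** Reword the second readiness item so that PEEP and FiO₂ must each be equal to or lower than on the previous day. A rise in either setting still fails the item. Leave the other four readiness criteria and the SBT pass criteria unchanged.

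Make the change at the next protocol amendment. It alters a few words in one bullet and needs no new procedures, no new patient data and no extra patients. The Synopsis describes Arm 1 monitoring in the past tense, so the change would probably reach only Arm 2 patients not yet weaned. The one drawback is that a small cohort may then span two versions of the rule. Flag patients weaned before the amendment in the ventilator-free-day listing so that the reader can see this.
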